7.1.4 Efficacy Measurements

7.1.4.1 Tumor Imaging and Assessment of Disease

The process for image collection and transmission to the blinded central imaging vendor can be found in the Site Imaging Manual (SIM). Tumor imaging should be acquired by computed tomography (CT, strongly preferred). Magnetic resonance imaging (MRI) should be used when CT is contraindicated or for imaging in the brain. However, when MRI is the standard of care at a site, MRI may be used whether or not CT is contraindicated. The same imaging technique regarding modality and use of contrast should be used in a subject throughout the trial to optimize the visualization of existing and new tumor burden.

Expedited confirmation of measurable disease based on RECIST 1.1 by the blinded central imaging vendor at screening will be used to determine subject eligibility. Confirmation of measurable disease by the central imaging vendor per RECIST 1.1 is required prior to subject randomization. Although RECIST 1.1 references a maximum of 5 target lesions in total and 2 per organ, Merck allows a maximum of 10 target lesions in total and 5 per organ.

All scheduled images for all study subjects from the sites will be submitted to the central imaging vendor. In addition, additional imaging (including other modalities) that are obtained at an unscheduled time point to determine disease progression, as well as imaging obtained for other reasons but captures radiologic progression, should be submitted to the central imaging vendor as well.

After the local site investigator-assessed first radiologic evidence of PD, the central imaging vendor will verify PD during the study. Expedited verification of radiologic PD by the central imaging vendor will be communicated to the study site and sponsor.

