8.4.1.2 Secondary

Objective Response Rate (ORR) – RECIST 1.1 by blinded central imaging vendor review

ORR is defined as the proportion of the subjects in the analysis population who have a CR or PR per RECIST 1.1.

Disease Control Rate (DCR) - RECIST 1.1 by blinded central imaging vendor review

DCR is defined as the proportion of subjects who have achieved CR, PR, or stable disease (SD) after ≥ 5 weeks (the start of the window for the first scheduled scan) based on assessments by the blinded central imaging vendor per RECIST 1.1.

Time to Progression (TTP) - RECIST 1.1 by blinded central imaging vendor review

TTP is defined as the time from randomization to the first documented disease progression per RECIST 1.1. See Section 8.6.1 for definition of censoring.

Duration of Response (DOR) - RECIST 1.1 by blinded central imaging vendor review

For subjects who demonstrate CR or PR, DOR is defined as the time from first documented evidence of CR or PR per RECIST 1.1 until disease progression per RECIST 1.1 or death due to any cause, whichever occurs first. See Section 8.6.1 for definition of censoring.

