In order to evaluate the robustness of the PFS endpoint per RECIST 1.1 by the blinded central imaging vendor review, 2 sensitivity analyses will be performed with a different set of censoring rules. The first sensitivity analysis is the same as the primary analysis except that (1) the date of documented PD or death will be the progression date, regardless of whether or not new anti-cancer treatment is initiated and (2) it censors at the last disease assessment, regardless of whether or not new anti-cancer treatment is initiated if no PD and no death occur. The second sensitivity analysis is the same as the first sensitivity analysis, except that it considers discontinuation of treatment due to reasons other than complete response or initiation of an anti-cancer treatment subsequent to discontinuation of study-specified treatment, whichever occurs later, to be a PD event for subjects without documented PD or death. The censoring rules for primary and sensitivity analyses are summarized in [Table 8](#).

Table 8 Censoring Rules for Primary and Sensitivity Analyses of PFS

| Situation | Primary Analysis | Sensitivity Analysis 1 | Sensitivity Analysis 2 |
|---|---|--|---|
| PD or death documented after ≤ 1 missed disease assessment, and before new anti-cancer therapy, if any | Progressed at date of documented PD or death | Progressed at date of documented PD or death | Progressed at date of documented PD or death |
| PD or death documented after ≥ 2 consecutive missed disease assessments or after new anti-cancer therapy | Censored at last disease assessment prior to the earlier date of ≥ 2 consecutive missed disease assessment and new anti-cancer therapy, if any | Progressed at date of documented PD or death | Progressed at date of documented PD or death |
| No PD and no death; and new anti-cancer therapy is not initiated | Censored at last disease assessment | Censored at last disease assessment | Progressed at treatment discontinuation due to reasons other than complete response; otherwise censored at last disease assessment if still on study or completed study therapy |
| No PD and no death; new anti-cancer therapy is initiated | Censored at last disease assessment before new anti-cancer therapy | Censored at last disease assessment | Progressed at date of new anti-cancer therapy |

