8.6.1.5 Time to Progression

The non-parametric Kaplan-Meier method will be used to estimate the TTP curve in each treatment group. A stratified Cox proportional hazard model with Efron's method of tie handling will be used to estimate the magnitude of the treatment difference (i.e., hazard ratio) between the treatment arms. The hazard ratio and its 95% confidence interval from the stratified Cox model with Efron's method of tie handling and with a single treatment covariate will be reported. The stratification factors used for randomization (see Section 5.4) will be applied to both the stratified log-rank test and the stratified Cox model. The same 5 strata defined for the PFS analysis (see Section 8.6.1.1) will be used for the TTP analysis.

Since disease progression is assessed periodically, progressive disease (PD) can occur any time in the time interval between the last assessment where PD was not documented and the assessment when PD is documented. For the analysis, for the subjects who have PD, the true date of disease progression will be approximated by the date of the first assessment at which PD is objectively documented per RECIST 1.1 by blinded central imaging vendor review, regardless of discontinuation of study drug. Unlike in PFS analysis, death is not considered as an event. Censoring rules for TTP are summarized in [Table 9](#).

Table 9 Censoring Rules for TTP

| Situation | Primary Analysis |
|---|--|
| Death only | Censored at date of randomization or date of last non-PD disease assessment, whichever is later |
| No PD and no death; new anticancer treatment is not initiated | Censored at last non-PD disease assessment |
| No PD and no death; new anticancer treatment is initiated | Censored at last non-PD disease assessment before new anticancer treatment |
| PD documented after ≤ 1 missed disease assessment | Progressed at date of documented PD |
| PD documented after ≥ 2 missed disease assessments | Censored at last disease assessment prior to the ≥ 2 consecutive missed disease assessments |

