8.6.1.6 Duration of Response

Subjects who achieved CR or PR and are alive, have not progressed, have not initiated new anti-cancer treatment, have not missed ≥ 2 consecutive missed disease assessments, and have not been determined to be lost to follow-up are considered ongoing responders at the time of analysis.

The non-parametric Kaplan-Meier method will be used to estimate the DOR curve in each treatment group; estimates and 95% CIs at specific duration time points will be provided.

Censoring rules for DOR are summarized in [Table 10](#).

Table 10 Censoring Rules for DOR

| Situation | Date of Progression or Censoring | Outcome |
|--|--|-------------------------|
| No progression nor death, no new anti-cancer therapy initiated | Last adequate disease assessment | Censor (non-event) |
| No progression nor death, new anti-cancer therapy initiated | Last adequate disease assessment before new anti-cancer therapy initiated | Censor (non-event) |
| Death or progression after ≥ 2 consecutive missed disease assessments or after new anti-cancer therapy. | Earlier date of last adequate disease assessment prior to ≥ 2 missed adequate disease assessments and new anti-cancer therapy, if any | Censor (non-event) |
| Death or progression after ≤ 1 missed adequate disease assessments and before new anti-cancer therapy, if any | PD or death | End of response (Event) |

Subjects are considered to have an ongoing response if censored, alive, have not progressed, have not started a new anti-cancer therapy, have not missed ≥ 2 consecutive disease assessments, and have not been determined to be lost to follow-up.

Table 11 summarizes the primary analysis approach for primary and secondary efficacy endpoints. Sensitivity analysis methods are described above for each endpoint.

Analyses of the DCR, TTP, and DOR data will be performed at the time of the interim and final analysis of OS.

The strategy to address multiplicity issues with regard to multiple efficacy endpoints, multiple populations, and interim analyses is described in Section 8.7 Interim Analyses and in Section 8.8 Multiplicity.

Table 11 Analysis Strategy for Key Efficacy Endpoints

| Endpoint/Variable (Description, Time Point) | Statistical Method [†] | Analysis Population | Missing Data Approach |
|---|--|---------------------|--|
| Primary Hypothesis #1 | | | |

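### Time to progression (Table 9) has no single rule for new anti-cancer therapy, so censoring among switchers depends on what happens after the switch

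*Combined protocol and SAP*

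**What the plan says.** Section 8.4.1.2 defines the endpoint without reference to new therapy: "TTP is defined as the time from randomization to the first documented disease progression per RECIST 1.1". Table 9 in Section 8.6.1.5 then sets the handling:

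- **Event row:** "PD documented after ≤ 1 missed disease assessment | Progressed at date of documented PD". New therapy is not mentioned. The text above the table dates the event at the first assessment at which "PD is objectively documented per RECIST 1.1 by blinded central imaging vendor review, regardless of discontinuation of study drug".
- **Alive without PD, new treatment started:** "Censored at last non-PD disease assessment before new anticancer treatment".
- **Death without PD:** censored at randomization or the last non-PD assessment, whichever is later, with no cut-off at new therapy.
- **PD after two or more missed assessments:** censored before the gap; new therapy is not mentioned.

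The only departure from PFS that the section states is that death is not an event. For PFS, Table 8 has a row for PD or death after two or more "consecutive missed disease assessments or after new anti-cancer therapy", which the primary analysis censors. PFS sensitivity analysis 1 ignores new therapy throughout.

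Scheduled imaging ends when new anti-cancer treatment starts (Sections 7.1.4.1.2, 7.1.4.1.3 and 7.1.6.3.2). Section 7.1.4.1 nevertheless asks sites to send unscheduled scans made to determine progression, and says that "imaging obtained for other reasons but captures radiologic progression, should be submitted to the central imaging vendor as well".

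**The concern.** Take three subjects who are identical on the day they start new therapy. One later has centrally read PD, one dies without PD, and one stays alive without PD. Table 9 lets the first two carry post-switch time into the analysis and cuts the third back to before the switch. Kaplan-Meier and Cox estimation assume that whether a subject is still at risk at a given time does not depend on what happens to that subject later. Here it does. If switching or post-switch scanning differs between arms, or progression rates differ, the TTP curves and hazard ratio can be distorted. TTP and PFS could also diverge on the same scans for reasons unrelated to treatment.

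**Working it through.** **Step 1. Compare the rules for a subject who starts new therapy before central PD.**

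| Later course | TTP, Table 9 | PFS primary, Table 8 | PFS sensitivity 1, Table 8 |
|---|---|---|---|
| PD, at most one missed assessment | Event at the post-switch date | Censored at last assessment before the switch | Event at the PD date |
| Death without PD | Censored at last non-PD scan, even if post-switch | Censored at last assessment before the switch | Event at death |
| Alive without PD | Censored at last non-PD scan before the switch | Censored at last assessment before the switch | Censored at last assessment, post-switch included |

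Each PFS column treats new therapy the same way in every row. The TTP column does not.

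**Step 2. Does the missed-assessment row close the gap?** Only in part. With at most one missed assessment, PD can be documented about 2 × 6 = 12 weeks after the last scan on the on-treatment schedule, and about 2 × 12 = 24 weeks after it on the off-treatment schedule. The plan does not say which schedule counts once new therapy has ended required imaging.

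**Step 3. Size.** The plan gives no event count, hazard ratio or power for TTP, so there is no figure to reproduce. An illustrative simulation compared Table 9 as written with censoring every switcher at the last scan before the switch.

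- From the documents: 2:1 allocation, 6-week scans, a control median of 2.5 months (the PFS figure in Section 8.9, used as a stand-in), and follow-up of 6 to 22 months.
- Assumed: monthly switch rates, the share of switchers still scanned every 6 weeks, switching unrelated to prognosis, and no effect of the new therapy.
- Left out: deaths and the missed-assessment row, so large shifts are easier to produce.
- 400,000 subjects per scenario.

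| True HR | Switch rate per month, control / pembrolizumab | Share scanned | HR, Table 9 | HR, one rule | Difference |
|---|---|---|---|---|---|
| 0.6 | 0.20 / 0.20 | 0% | 0.647 | 0.647 | 0.000 |
| 0.6 | 0.10 / 0.05 | 50% | 0.645 | 0.647 | −0.002 |
| 0.6 | 0.20 / 0.05 | 50% | 0.631 | 0.647 | −0.016 |
| 0.6 | 0.20 / 0.20 | 25% | 0.663 | 0.646 | +0.017 |
| 0.6 | 0.20 / 0.20 | 100% | 0.693 | 0.641 | +0.052 |
| 1.0 | 0.20 / 0.05 | 50% | 0.964 | 0.996 | −0.032 |
| 1.0 | 0.20 / 0.05 | 100% | 0.951 | 0.989 | −0.038 |

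Only the difference column matters. The one-rule value sits near 0.645 rather than 0.60 because event dates fall on a 6-week grid and ties were handled by Breslow's method (the plan uses Efron's). Six weeks is 42/30.4375 = 1.38 months. The per-interval progression probabilities are 1 − exp(−0.277 × 1.38) = 0.318 in control and 1 − exp(−0.6 × 0.277 × 1.38) = 0.205 on pembrolizumab, and 0.205/0.318 = 0.645.

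**Step 4. What the largest shift requires.** The control progression rate is ln 2/2.5 = 0.277 per month. A switch rate of 0.20 per month then means 0.20/(0.20 + 0.277) = 42% of control subjects switch before PD. On pembrolizumab it means 0.20/(0.20 + 0.6 × 0.277) = 55%. All of them would have to go on being scanned every 6 weeks.

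**Step 5. A setting closer to the protocol.** A second simulation added deaths, the missed-assessment row and a single incidental scan within 9 months of the switch (assumed). The shift was 0.003 to 0.008 with 27% of pembrolizumab and 9% of control subjects switching, and at most about 0.01 with higher switching in control.

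**The case against.** The strongest reply is that the route is narrow. Required imaging stops at new therapy, the subject moves to survival follow-up by telephone or visit, and Section 8.6.1.2 describes switching after central verification of PD, when the TTP event already exists. The missed-assessment row removes some late scans. TTP has no hypothesis, no alpha, no power statement and no row in Table 11, and Section 8.6.1 already urges caution with nominal p-values. All of this stands, and it is why the point is minor. It does not remove the problem. A subject moves to survival follow-up on site-assessed PD (Section 7.1.6.3.3), so new therapy can precede a central PD call, and Section 7.1.4.1 gives later scans a way to reach the vendor.

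Four stronger readings are tempting, and the documents do not support them.

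- **Post-switch time counts only for subjects who progress.** The death-without-PD row also keeps it. Nor are post-switch non-PD scans barred from submission: Section 7.1.4.1.2 asks for all supplemental imaging. It is Table 9 that discards them, and only for switchers alive without PD.
- **Table 9 breaks a requirement to follow the PFS rule.** No text says that the two must match. This is an unexplained inconsistency, probably a drafting omission.
- **A shift of 0.04 or more is to be expected.** A continuous-time simulation reached 0.04 (0.60 to 0.64) only with 28% of pembrolizumab and 9% of control subjects switching. Section 8.6.1.2 points the other way, expecting control subjects to discontinue earlier and possibly switch. With similar or modestly higher control switching, that simulation gave 0.00 to 0.01.
- **Duration of response has the same error.** Table 10 excludes events after new therapy. Its wording "Earlier date of last adequate disease assessment prior to" a gap and new therapy can be parsed two ways, which is an ambiguity only.

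**Conclusion.** The inconsistency is real on the text of Table 9. Among subjects who start new therapy, the censoring date depends on the later outcome, and the rule matches neither the primary PFS analysis nor PFS sensitivity analysis 1. The bias can go in either direction. It is zero with no scanning after new therapy, about 0.00 to 0.01 on the TTP hazard ratio with occasional incidental scans, and up to about 0.05 only with heavy switching and continued scanning, which the protocol does not schedule. These sizes rest on assumed switch and scan rates and on the PFS control median standing in for TTP. The confirmatory tests of PFS, OS and ORR are unaffected. This is a minor correction to a secondary endpoint.

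**What to change.** Apply one new-therapy rule to every row of Table 9:

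- **Event row:** count PD only if it follows at most one missed assessment and precedes any new anti-cancer therapy.
- **Last row:** extend it to PD documented after two or more "consecutive missed disease assessments or after new anti-cancer therapy", censored at the last disease assessment before the earlier of the two.
- **Death without PD:** censor at the later of randomization and the last non-PD assessment made before any new anti-cancer therapy.
- **Alive without PD:** no change.

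Add a TTP sensitivity analysis that ignores new therapy in all rows, as PFS sensitivity analysis 1 does. Changing the two PD rows alone would not be enough, because switchers who die would still keep post-switch scans that living switchers lose.

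The cost is three edited rows, one extra analysis and somewhat fewer TTP events. In the scenario with true HR 0.6, 0.20 per month switching in both arms and 25% scanned, the share of subjects with an event falls from 0.537 to 0.420. No new data are needed. Section 8.0 allows changes to non-confirmatory analyses to be recorded in the supplemental SAP if made before any analysis is run. Stating in Table 10 that censoring is at the last adequate assessment before new therapy is an optional clarification.

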8.6.1.6 Duration of Response

Subjects who achieved CR or PR and are alive, have not progressed, have not initiated new anti-cancer treatment, have not missed ≥ 2 consecutive missed disease assessments, and have not been determined to be lost to follow-up are considered ongoing responders at the time of analysis.

The non-parametric Kaplan-Meier method will be used to estimate the DOR curve in each treatment group; estimates and 95% CIs at specific duration time points will be provided.

Censoring rules for DOR are summarized in [Table 10](#).

Table 10 Censoring Rules for DOR

| Situation | Date of Progression or Censoring | Outcome |
|--|--|-------------------------|
| No progression nor death, no new anti-cancer therapy initiated | Last adequate disease assessment | Censor (non-event) |
| No progression nor death, new anti-cancer therapy initiated | Last adequate disease assessment before new anti-cancer therapy initiated | Censor (non-event) |
| Death or progression after ≥ 2 consecutive missed disease assessments or after new anti-cancer therapy. | Earlier date of last adequate disease assessment prior to ≥ 2 missed adequate disease assessments and new anti-cancer therapy, if any | Censor (non-event) |
| Death or progression after ≤ 1 missed adequate disease assessments and before new anti-cancer therapy, if any | PD or death | End of response (Event) |

Subjects are considered to have an ongoing response if censored, alive, have not progressed, have not started a new anti-cancer therapy, have not missed ≥ 2 consecutive disease assessments, and have not been determined to be lost to follow-up.

Table 11 summarizes the primary analysis approach for primary and secondary efficacy endpoints. Sensitivity analysis methods are described above for each endpoint.

Analyses of the DCR, TTP, and DOR data will be performed at the time of the interim and final analysis of OS.

The strategy to address multiplicity issues with regard to multiple efficacy endpoints, multiple populations, and interim analyses is described in Section 8.7 Interim Analyses and in Section 8.8 Multiplicity.

Table 11 Analysis Strategy for Key Efficacy Endpoints

| Endpoint/Variable (Description, Time Point) | Statistical Method [†] | Analysis Population | Missing Data Approach |
|---|--|---------------------|--|
| Primary Hypothesis #1 | | | |
| PFS per RECIST 1.1 by blinded central imaging vendor review | Test: Stratified Log-rank test Estimation: Stratified Cox model with Efron's tie handling method | ITT | 
 Primary censoring rule Sensitivity analysis 1 Sensitivity analysis 2 (More details are in Table 8) |
| Primary Hypothesis #2 | | | |
| OS | Test: Stratified Log-rank test Estimation: Stratified Cox model with Efron's tie handling method | ITT | Censored at last known alive date |
| Secondary Hypothesis #1 | | | |
| ORR per RECIST 1.1 by blinded central imaging vendor review | Stratified M & N method [‡] | ITT | Subjects with missing data are considered non-responders |

[†] Statistical models are described in further detail in the text. For stratified analyses, the stratification factors used for randomization (see Section 5.4) will be applied to the analysis model.

[‡] Miettinen and Nurminen method [49]

8.6.2 Statistical Methods for Safety Analyses

Safety and tolerability will be assessed by clinical review of all relevant parameters including AEs, laboratory tests, vital signs, etc.

Tiered Approach

The analysis of safety results will follow a tiered approach ([Table 12](#)). The tiers differ with respect to the analyses that will be performed. For this protocol, there are no Tier 1 events.

Tier 2 parameters will be assessed via point estimates with 95% confidence intervals provided for between-group comparisons; only point estimates by treatment group are provided for Tier 3 safety parameters.

AEs (specific terms as well as system organ class terms) will be classified as belonging to "Tier 2" or "Tier 3", based on the number of events observed. Membership in Tier 2 requires that at least 4 subjects in any treatment group exhibit the event; all other AEs and predefined limits of change will belong to Tier 3.

The threshold of at least 4 events was chosen because the 95% confidence interval for the between-group difference in percent incidence will always include zero when treatment groups of equal size each have less than 4 events and thus would add little to the interpretation of potentially meaningful differences. Because many 95% confidence intervals may be provided without adjustment for multiplicity, the confidence intervals should be regarded as a helpful descriptive measure to be used in review, not a formal method for assessing the statistical significance of the between-group differences in AEs and predefined limits of change.

Continuous measures such as changes from baseline in laboratory, vital signs, that are not pre-specified as Tier-1 endpoints will be considered Tier 3 safety parameters. Summary statistics for baseline, on-treatment, and change from baseline values will be provided by treatment group in table format.

In addition, the broad clinical and laboratory AE categories consisting of the percentage of subjects with any AE, any drug related AE, any Grade 3-5 AE, any serious AE, any AE which is both drug-related and Grade 3-5, any AE which is both serious and drug-related, dose modification due to AE, and who discontinued due to an AE, and death will be considered Tier 2 endpoints.

The 95% confidence intervals will be provided for between-treatment differences in the percentage of subjects with Tier 2 events; these analyses will be performed using the Miettinen and Nurminen method [49], an unconditional, asymptotic method.

Table 12 Analysis Strategy for Safety Parameters

| Safety Tier | Safety Endpoint | 95% CI for Treatment Comparison | Descriptive Statistics |
|-------------|--|---------------------------------|------------------------|
| Tier 2 | Any AE | X | X |
| | Any Serious AE | X | X |
| | Any Grade 3-5 AE | X | X |
| | Any Drug-Related AE | X | X |
| | Any Serious and Drug-Related AE | X | X |
| | Any Grade 3-5 and Drug-Related AE | X | X |
| | Dose Modification due to AE | X | X |
| | Discontinuation due to AE | X | X |
| | Death | | |
| | Specific AEs, SOCs, or PDLCs (incidence ≥ 4 of subjects in one of the treatment groups) | X | X |
| Tier 3 | Specific AEs, SOCs or PDLCs [‡] (incidence < 4 of subjects in all of the treatment groups), AEOSI | | X |
| | Change from Baseline Results (Labs, ECGs, Vital Signs) | | X |

AE = adverse event; AEOSI = adverse events of special interest; ECG = electrocardiogram; PDLC = pre-defined limit of change; SOC = system organ class.

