2.0 TRIAL DESIGN

2.1 Trial Design

This is a double-blind randomized Phase III trial of pembrolizumab (MK-3475) plus best supportive care (BSC) versus placebo plus BSC in previously systemically treated subjects with a hepatocellular carcinoma (HCC) diagnosis confirmed by radiology, histology, or cytology (fibrolamellar and mixed hepatocellular/cholangiocarcinoma subtypes are not eligible). To be eligible, subjects must have documented objective radiographic progression of disease (PD) during or after treatment with sorafenib, or else be intolerant of sorafenib as defined in Section 5.1.2. They also must have disease not amenable to a curative treatment approach (e.g., transplant, surgery, or ablation). Subjects must have at least one measurable lesion that is confirmed by the blinded central imaging vendor per Response Evaluation Criteria in Solid Tumors (RECIST) 1.1, Child-Pugh liver class A, an Eastern Cooperative Oncology Group (ECOG) performance score of 0 or 1, and predicted life expectancy of > 3 months. Subjects will be enrolled regardless of tissue programmed death ligand 1 (PD-L1) biomarker status. Subjects will not be required to provide a tumor tissue sample for biomarker analysis, but are strongly urged to do so if tissue is available. Approximately 408 subjects will be randomized at a 2:1 ratio to receive pembrolizumab 200 mg IV plus BSC every 3 weeks (Q3W) or placebo IV plus BSC (Q3W).

Enrollment of subjects in the Asian population will be capped to approximately 30% of the study population (approximately 122 subjects total); hepatitis B subjects will be capped also to approximately 30% of the study population (approximately: 122 subjects total; 61 from Asia without Japan population [i.e., 15% of 408]; and 61 subjects from non-Asian with Japan population [i.e., 15% of 408]). Additionally, the sorafenib-intolerant population will be capped at approximately 20% within each region (approximately: 82 subjects total; 25 from Asia without Japan population [i.e., 20% of 122]; and 57 from non-Asia with Japan population [i.e., 20% of 286]), to ensure that the study population is representative of the U.S. population.

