5.3 Randomization

Treatment allocation/randomization will occur centrally using an interactive voice response system / integrated web response system (IVRS/IWRS). There are 2 treatment arms. Subjects will be assigned randomly in a 2:1 ratio to pembrolizumab and placebo, respectively.

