8.5.2 Safety Analysis Populations

The All Subjects as Treated (ASaT) population will be used for the analysis of safety data in this study. The ASaT population consists of all randomized subjects who received at least one dose of study treatment. Subjects will be included in the treatment group corresponding to the study treatment they actually received for the analysis of safety data using the ASaT population. For most subjects this will be the treatment group to which they are randomized. Subjects who take incorrect study treatment for the entire treatment period will be included in the treatment group corresponding to the study treatment actually received. Any subject who receives the incorrect study medication for one cycle but receives the correct treatment for all other cycles will be analyzed according to the correct treatment group and a narrative will be provided for any events that occur during the cycle for which the subject is incorrectly dosed.

At least one laboratory or vital sign measurement obtained subsequent to at least one dose of study treatment is required for inclusion in the analysis of each specific parameter. To assess change from baseline, a baseline measurement is also required.

Details on the approach to handling missing data for safety analyses are provided in Section 8.6 Statistical Methods.

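### Does the Tier 2 cut-off of 4 subjects fail because its rationale assumes equal arms while the trial randomizes 2:1?

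*Combined protocol and SAP*

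**What the plan says.** Section 8.6.2 sorts adverse events into tiers by frequency. The rule is: "Membership in Tier 2 requires that at least 4 subjects in any treatment group exhibit the event". Table 12 repeats it for specific terms ("incidence ≥ 4 of subjects in one of the treatment groups"). Tier 2 events get a 95% interval for the difference in percentages, and on the method the section says "these analyses will be performed using the Miettinen and Nurminen method [49], an unconditional, asymptotic method". Tier 3 events get point estimates by arm only. There are no Tier 1 events.

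The cut-off is defended on the ground that the interval "will always include zero when treatment groups of equal size each have less than 4 events", and so would add little. The same paragraph warns that many unadjusted intervals may be shown and that "the confidence intervals should be regarded as a helpful descriptive measure to be used in review", rather than as a formal test.

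On allocation, Section 2.1 states "Approximately 408 subjects will be randomized at a 2:1 ratio", and Section 5.3 states "Subjects will be assigned randomly in a 2:1 ratio to pembrolizumab and placebo, respectively". Section 8.5.2 defines the safety population: "The ASaT population consists of all randomized subjects who received at least one dose of study treatment". Its size by arm is not given.

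**The concern.** The only reason offered for withholding an interval below 4 subjects is a property of equal-sized groups, and this trial does not have equal-sized groups. Four subjects are 4/272 = 1.5% of a pembrolizumab arm of 272 but 4/136 = 2.9% of a placebo arm of 136. The same count is therefore a different threshold in each arm, and the text does not say so.

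If the property fails at 2:1, some events whose interval would exclude zero go into Tier 3 without one. A reader who trusts the rationale would wrongly take Tier 3 placement to mean that no such interval was possible. The matter would be serious if the hidden intervals showed harm from pembrolizumab.

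**Working it through.** **Inputs.** Total 408 and ratio 2:1 (Sections 2.1 and 5.3) give 408 × 2/3 = 272 and 408 × 1/3 = 136. Using these as the safety-population sizes is an assumption. The method is Miettinen-Nurminen, 95% two-sided, z = 1.96 (Section 8.6.2). The cut-off is 4 in any arm.

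**Formula.** The interval inverts a score test, so it excludes zero exactly when |Z| > 1.96, where

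Z = (x1/n1 − x2/n2) / √[ p(1−p)(1/n1 + 1/n2) × N/(N−1) ],

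with p = (x1+x2)/N and N = n1+n2. Arm 1 is pembrolizumab.

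**Step 1: the plan's statement for equal arms (204/204).**
- 3 vs 0: difference 3/204 = 1.47 points; p = 3/408 = 0.00735; standard error 0.00847; Z = 1.74; interval -0.40 to 4.24, which includes zero.
- 4 vs 0: difference 1.96 points; standard error 0.00977; Z = 2.01; interval 0.09 to 4.94, which excludes zero.

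The same switch between 3 and 4 occurs at 136 and at 272 per arm. At 204/204 no pair below 4 excludes zero. The plan's statement is reproduced for equal arms of these sizes.

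**Step 2: the same check at 272/136.** Here 1/272 + 1/136 = 0.01103.

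| Pembrolizumab vs placebo | Difference (points) | Z | 95% interval (points) | Zero |
|---|---|---|---|---|
| 0 vs 3 | −3/136 = −2.21 | −2.46 | −6.29 to −0.75 | excluded |
| 0 vs 2 | −2/136 = −1.47 | −2.00 | −5.21 to −0.06 | excluded, barely |
| 1 vs 3 | 1/272 − 3/136 = −1.84 | −1.77 | −5.95 to 0.22 | included |
| 3 vs 0 | 3/272 = 1.10 | 1.23 | −1.66 to 3.20 | included |

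For 0 vs 3, the standard error is √(0.00735 × 0.99265 × 0.01103 × 408/407) = 0.00898, and −0.02206/0.00898 = −2.46. Of the 15 pairs with fewer than 4 subjects per arm and at least one event, only 0 vs 3 and 0 vs 2 exclude zero.

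**Step 3: dependence on the assumed split (total 408).** The 0 vs 3 interval excludes zero at every split from 272/136 to 229/179 and first includes it at 228/180. The 0 vs 2 interval already includes zero at 268/140, with an upper limit of +0.001 points.

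**Step 4: the direction that matters for harm.** With no placebo events, 7 vs 0 gives −0.20 to 5.22 and 8 vs 0 gives 0.16 to 5.70. Zero is first excluded at 8, well above the cut-off. Patterns of 4 to 7 vs 0 already receive an interval, although it includes zero.

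**Step 5: the obvious repair, a cut-off of 4 on pembrolizumab or 2 on placebo.** Eight patterns would move to Tier 2 (0 to 3 on pembrolizumab with 2 or 3 on placebo). Six of them have intervals that include zero. The other two are 0 vs 2 and 0 vs 3, both favouring pembrolizumab. With no treatment effect, and given the total number of events, their chance frequencies are:
- two events, both on placebo: (136 × 135)/(408 × 407) = 18,360/166,056 = 11.1%;
- three events, all on placebo: (136 × 135 × 134)/(408 × 407 × 406) = 3.6%.

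Both exceed the nominal 2.5% tail, because the method is asymptotic and is applied here to two or three events.

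**The case for a change.** The strongest case for acting is that an analysis plan should not defend a trial-specific rule with a property of a design the trial does not use. Under the plan's own method the property fails, and for 0 vs 3 it fails at every split near 2:1. That a simple Wald interval for 0 vs 3 would include zero (−4.7 to 0.3 points) is no answer, because the plan names Miettinen-Nurminen. Correcting the sentence would cost almost nothing.

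The factual part of this stands: the justification does not carry over to 2:1. What does not stand is that anything in the analysis depends on it. The sentence is expressly limited to equal-sized groups, so it is inapplicable rather than false. The rule itself is clear and agrees between the text and Table 12, so every analyst would produce the same tables with or without the sentence. A 0 vs 3 pattern remains visible in the Tier 3 estimates by arm. Section 8.6.2 also places the broad categories (any event, serious, Grade 3-5, drug-related and so on) in Tier 2 without a count requirement.

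**Conclusion.** The rationale and the allocation do not match, but no change to the plan is needed. At 272/136 the mismatch affects two rare patterns, both with no events on pembrolizumab. One is robust (0 vs 3, −6.29 to −0.75 points). The other depends on the exact split (0 vs 2, −5.21 to −0.06 points, Fisher p = 0.11). No interval showing an excess on pembrolizumab is suppressed, and the intervals are descriptive and test nothing.

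Rewording the rationale would be an editorial tidy-up with no effect on any result or conclusion. The only change with an effect is an arm-specific cut-off. That is a debatable trade-off: it would set a lower display threshold for placebo than for the experimental drug, and the only zero-excluding intervals it adds favour pembrolizumab, partly on patterns that chance produces readily. Keeping a single cut-off of 4 is reasonable.

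This conclusion assumes safety-population sizes close to 2:1 of 408. Moving toward equal arms weakens the concern further, and at 204/204 it disappears.
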